### 7.1.2 Unsolicited Adverse Events

An unsolicited AE is an AE that was not solicited using a Subject eDiary and that was spontaneously communicated by a subject who has signed the informed consent.

Potential unsolicited AEs may be medically attended (defined as symptoms or illnesses requiring hospitalization, or emergency room visit, or visit to/by a health care provider), or were of concern to the subject. In case of such events, subjects will be instructed to contact the site as soon as possible to report the event(s). The detailed information about the reported unsolicited AEs will be collected by the qualified site personnel during the interview and will be documented in the subject’s records.

The period of observation for AEs extends from the time of informed consent until the subject either completes the specified safety follow-up period (Day 181) or at early study termination.

All unsolicited AEs that start during the treatment period (Day 1 to Day 29) will be recorded in the eCRF. During the follow-up (Day 30 to Day 181), unsolicited AEs that meet any reporting criterion (an SAE, AESI, AE leading to withdrawal or a MAAE) are to be recorded in the eCRF.

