### 8.1.2.1 Secondary Safety Endpoints

The secondary safety endpoints include the proportion of subjects reporting solicited and unsolicited adverse events:

- Percentage of subjects reporting a local and/or systemic adverse event for the 7 days following the vaccination (Day 1 to Day 7)
- Percentage of subjects reporting unsolicited adverse events for 28 days following vaccination (Day 1 to Day 29).
- Percentage of subjects reporting serious AEs, MA AEs, AEs leading to withdrawal or AESIs as collected during the study (Day 1 to End of Study).

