All adverse events will be characterized according to the date of occurrence related to the vaccination. If the start date is before the date of injection of study vaccine or indicated as on injection day but before injection, these events will not be considered as unsolicited adverse events and mapped to the medical history.

Note: If an adverse event start date is missing or unknown and no indication is provided on the timing, the adverse event will be considered as emergent.

When start and/or end dates of an adverse event are only partially known, adverse events will be categorized as emergent before, during, or after vaccination phase using the following rules:

• If the partial end date is before (<) the vaccination (i.e., year or year & month is/are before the study vaccination year or year & month) then the adverse event is pre-vaccination and the event will be mapped to the medical history.

16 MAR 2021 Final Version 2.0

• If the partial start date is equal or after (≥) the first study vaccination (i.e., year or year and month is/are after or the same as the first study injection year or year and month) then the adverse event is emergent during vaccination phase.

All adverse events emergent during vaccination phase will categorized as occurring during the period of 28 days following vaccination based on the start date. If start date is missing or incomplete, events will be counted as yes during the period of 28 days following vaccination.

The **maximum event severity** is the greatest severity associated with a preferred term (PT) for a reported adverse event according to the following order: Mild < Moderate < Severe.

Vaccination-related Adverse Events are those for which the cause has been evaluated by the investigator, and recorded as possibly related, probably related or unknown/ missing.

Prior and Concomitant Medications

All medications will be characterized according to the start and end date of occurrence related to the vaccination as follows:

- **Pre-vaccination**: start date before the date of injection of study vaccine.
- **Concomitant:** start date before vaccination but continued after vaccination or start date after vaccination. The period Day 1- 29 will be labeled if in addition, the start date is on or before Day 29.

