13.3 Unsolicited Adverse Events

This analysis applies to all AE's occurring during the study, judged either as probably related, possibly related, or not related to vaccination by the investigator, recorded in the AE eCRF, with a start date on (but with onset after vaccination) or after the date of vaccination. AE starting prior to study vaccination will only be listed.

The original verbatim terms used by investigators to identify adverse events in the eCRFs will be mapped to preferred terms using the MedDRA dictionary.

The adverse events will then be grouped by MedDRA preferred terms into frequency tables according to system organ class. All reported AEs, as well as AEs judged by the investigator as at

16 MAR 2021 Final Version 2.0

least possibly related to study vaccine, will be summarized according to system organ class and the preferred term within system organ class. These summaries will be presented by the vaccination group. When an AE occurs more than once for a subject, the maximal severity and strongest relationship to the vaccine group will be counted.

The assignment to safety follow-up time intervals will be done by day of onset and not by days ongoing/persisting.

The summaries will be presented by period of onset (Day 1 to Day 29, Day 30 to end of study or Day 1 to end of study). An overview summary will be created by time -period with number and % of subjects with the following categories:

- AE
- AE by maximum severity
- Related (i.e. at least possible) AE
- SAEs
- Related SAEs
- AESIs
- MAAEs
- AEs leading to withdrawal from study
- Deaths.

The following summaries will be produced by SOC and Preferred Term and by time-period (Day 1 to Day 29, Day 30 to end of study or Day 1 to end of study):

- AEs
- AEs by maximum severity
- AEs that are possibly or probably related to the vaccine
- SAEs
- SAEs that are possibly or probably related to the vaccine

- AESIs
- MAAEs
- AEs leading to withdrawal
- Deaths.

Data listings of all adverse events will be provided by subject. In addition, adverse events in the categories above will be provided as listed data.

All tables will be produced overall and by age subgroup.

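### SAP 8.7 counts an adverse event with an incomplete start date in Day 1–29 even when the recorded month or year proves it began later

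*SAP*

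**What the plan says.** SAP 8.7 (Unsolicited Adverse Events) handles partial dates in three moves.

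- It announces the classes: "adverse events will be categorized as emergent before, during, or after vaccination phase using the following rules". Two rules follow. A partial end date before vaccination makes the event pre-vaccination. A partial start date makes it emergent during the vaccination phase if the "year or year and month is/are after or the same as the first study injection year or year and month". No rule leads to the third class, after.
- Events in the during class are then placed in or out of the 28-day period by start date.
- For dates that are not complete: "If start date is missing or incomplete, events will be counted as yes during the period of 28 days following vaccination".

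SAP 13.3 tabulates unsolicited events by period of onset: Day 1–29, Day 30 to end of study, and Day 1 to end of study. It adds: "The assignment to safety follow-up time intervals will be done by day of onset and not by days ongoing/persisting".

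Protocol 8.1.2.1 makes the Day 1–29 percentage of subjects with unsolicited events a secondary safety endpoint. From Day 30, Protocol 7.1.2 limits what is captured: "unsolicited AEs that meet any reporting criterion (an SAE, AESI, AE leading to withdrawal or a MAAE) are to be recorded in the eCRF".

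**The concern.** An early default is sensible when the timing of an event is unknown. Here it also applies when the timing is known well enough, so it overrides recorded information that places onset after Day 29. Two consequences follow.

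- Day 1–29 tables and the secondary endpoint can include follow-up events.
- Day 30-to-end tables lose the same events. These are exactly the categories that the follow-up period exists to capture: SAEs, AESIs, medically attended events and withdrawals due to an event.

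The analysis runs in two steps (SAP 14), and the first uses data only to Visit 3. A Day 1–29 percentage could therefore rise between the two reports because of events that began after Day 29.

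**Working it through.** The documents give no figure for this rule, so there is none to reproduce. The check is a literal reading followed by calendar arithmetic.

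**1. Follow one event through the rule.** Assume vaccination on 15 October 2020 and a medically attended event with start date January 2021, day unknown.

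- Day 29 = 15 October + 28 days = 12 November 2020.
- 1 January 2021 is Day 79 and 31 January 2021 is Day 109, so onset lies in Day 79–109.
- Under SAP 8.7, January 2021 is after the vaccination month, so the event is in the during class.
- Its start date is incomplete, so it is counted in the 28-day period, although no day in January 2021 falls there.

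**2. Look for an override.** SAP 13.3 and Protocol 8.4.3.1.3 both split at Day 29/30, and neither has a partial-date rule. The SAP 13.3 sentence on onset contrasts onset with persistence and does not address partial dates. Complete dates are handled correctly.

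**3. How often does a known month settle the matter?**

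- Day 30 to Day 181 is 181 − 30 + 1 = 152 days.
- A month has at most 31 days, so the month containing Day 29 ends no later than Day 29 + 30 = Day 59. Every onset from Day 60 therefore lies in a month wholly after Day 29: 181 − 60 + 1 = 122 days, and 122/152 = 80%.
- At best, Day 29 is the last day of its month and all 152 days qualify (100%).
- Over all 731 vaccination dates in 2020–2021 the mean is 137.3 days, and 137.3/152 = 90.3%.

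**4. And a known year only?** This depends on the vaccination month. Using 2021 dates, the share of Day 30–181 that is provably late is 0% for vaccination in January–June, about 48% in September, 68% in October and 89% in November.

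Steps 3 and 4 give shares of calendar days, not of events. The documents state no vaccination dates, so the averages and the year-only figures are illustrations. The 122–152 range holds for any vaccination date.

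**5. Effect per moved subject.** Arms are about 120 and age strata about half of that, 60.

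- 1/120 = 0.83 points per arm; 1/60 = 1.67 points per age stratum.
- Three or five such subjects in one arm would give 3/120 = 2.5 or 5/120 = 4.2 points.
- A subject who already has a Day 1–29 event adds nothing to the overall percentage.

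**The case against.** The strongest case is that this is a drafting gap with little effect.

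- *The unused after class may simply be empty.* Vaccination phase is not defined. If it means all time after vaccination, the missing upper limit is no error, because the Day 29 cut comes in the next step. This is fair and makes that part a wording matter. It does not help the 28-day sentence, which misplaces the event on either reading.
- *Few events are exposed.* SAEs and AESIs are notified within 24 hours, medically attended events involve a healthcare contact, medical records are reviewed, and queries can be raised. This stands. Medically attended events recalled at the Day 91 call or the Day 181 visit are the most plausible case.
- *The first report is nearly free of the problem.* This also stands: the Visit 3 window ends three days after Day 29, so almost no late event can be in the first-step data.
- *The medication rule is not a true parallel.* SAP 8.7 says of medications: "The period Day 1- 29 will be labeled if in addition, the start date is on or before Day 29". That rule does not deal with incomplete dates either. It shows that a Day 29 limit was in mind in the same section, and no more.
- *The default is conservative.* It is for Day 1–29 when timing is ambiguous. It is not for Day 30-to-end, where it understates events.

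These points bear on weight. None supplies the missing exception.

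**Conclusion.** The rule is wrong as written: it assigns events to a period that their own recorded dates exclude. The fault lies in the whole-study analysis and concerns late SAEs, AESIs, medically attended events and withdrawals with an incomplete start date. It can affect the by-period tables of SAP 13.3 and the Day 1–29 secondary endpoint.

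The protocol endpoint for those four categories runs from Day 1 to the end of the study and cannot change; nor can the Day 1-to-end summaries or the listings. No hypothesis is tested on safety and the rule does not differ by arm, so no study conclusion is shown to depend on it. The total effect cannot be estimated, because the documents give no number of incomplete dates. The case for correction rests on a definite error that is cheap to remove.

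**What to change.** Replace the 28-day sentence in SAP 8.7 with:

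> If the start date is incomplete, count the event in Day 1–29 unless the known part of the date shows onset after Day 29; in that case assign it to Day 30 to end of study. Completely missing start dates default to Day 1–29.

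In the same edit, define vaccination phase and either delete the unused after class or give it a rule.

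The cost is a short SAP edit and one programming condition, with no new data and no protocol amendment. Missing and ambiguous dates keep the early default. SAP 16 shows that version 2.0 already revised how section 8.7 treats events before vaccination, so this is a change of the same kind.

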8.8 Analysis Software

All analyses will be performed using SAS Software version 9.5 or higher.

9. STUDY SUBJECTS

9.1 Disposition of Subjects and Withdrawals

Document #: FORM2-000092701, Ed: 3.0

16 MAR 2021 Final Version 2.0

All randomized subjects will be accounted for in this study. The numbers and percentages of subjects in each analysis set, study withdrawals, subgroups, and major protocol deviations will be presented. Number of subjects per site will be presented by vaccine group and overall for All Enrolled Set.

The time in days (i.e. date of last assessment minus date of vaccination plus 1) the subjects are under observation for safety will be summarized by vaccine group and overall.

16 MAR 2021 Final Version 2.0

10. DEMOGRAPHICS AND OTHER BASELINE CHARACTERISTICS

In general, all tables related to baseline characteristics should include a Total column across vaccine groups.

10.1 Demographics

Age, height, weight, body mass index and Hak score will be summarized by reporting the mean, standard deviation, median and range, and will be calculated by vaccine group and overall.

In addition, the frequencies of age categories will be reported as 50-64 and ≥ 65 years old (age as a randomization stratum) and 50-64, 65-74, and 75-84, and ≥ 85 years old. The number and percentages of subjects by sex, ethnic origin, race, previous vaccination history (in past 3 years), and comorbidity risk (Hak score <50 and \ge 50) will be presented by vaccine group and overall.

Demographic data will be tabulated for the All Enrolled, FAS, PPS and Safety sets.

The distribution across all stratification factors (age subgroup * previous vaccination history) will be presented by vaccine group and overall. This table will be presented based on the IRT data and – if different – also for the actual eCRF data.

10.2 Medical History

The numbers and percentages of subjects with medical history will be presented by Medical Dictionary for Regulatory Activities (MedDRA) system organ class (SOC) and preferred term (PT) by vaccine group and overall. Medical history data will be tabulated for the All Enrolled, FAS, PPS and Safety Sets.

16 MAR 2021 Final Version 2.0

11. IMMUNOGENICITY ANALYSIS

The immunogenicity analysis will be descriptive in nature and focus on the estimation of the treatment effects of aQIVc versus each of the three other vaccines.

11.1 Blood samples

The number and percentages of subjects with and without blood draws will be summarized overall and by vaccine group. Data will be tabulated for the All Enrolled Set.

11.2 Primary Objectives Analysis

The primary endpoints in terms of HI antibody response against homologous cell-derived vaccine strains (A/H1N1, A/H3N2, B/Yamagata and B/Victoria) are defined as:

- Geometric Mean Titer (GMT): Geometric mean of HI antibodies at Day 29 and Day 1;
- Geometric Mean Fold Increase (GMFI): The Geometric mean of the fold increase in serum HI GMTs post-vaccination (Day 29) compared to pre-vaccination (Day 1);
- Percentages of subjects with HI titers \geq 1:40 at Day 29 and Day 1;
- Percentage of subjects with seroconversion (defined as $a \ge 4$ -fold increase in titer post-vaccination in those with pre-vaccination titer above the LLOQ (1:10), or a post-vaccination titer $\ge 1:40$ for subjects with baseline titer below the LLOQ (1:10) for HI antibodies at Day 29).

Note that the HI assay could be replaced by the MN assay due to a lack of agglutination.

In addition, reverse cumulative distribution plots will be generated to display the distribution of the antibody responses at Day1 and Day 29 for each of the vaccine groups. The x-axis represents the immunogenicity values, and the scale of the axis is logarithmic. The y-axis represents the percentage of subjects having at least that immunogenicity value. Due to the discrete values of antibody response, the plot will show a step-wise function. The figures begin at 100%, and then descends to the lowest point on the curve, which is the percentage of subjects having an immunogenicity value equal to the highest observed value.

No hypothesis testing will be applied.

Effective Date: See System Metadata

16 MAR 2021 Final Version 2.0

Geometric Mean Titer

Summary statistics (geometric mean, 95% confidence interval of GMT, minimum, median, maximum) of the titers will be presented by strain, assessment (Day 1 or Day 29) and vaccine group.

The analysis model used for the comparison of the HI (or MN) GMT between aQIVc and the other three vaccine groups will be done using a general linear model on log-transformed (base 10) Day 29 titers as the outcome variable and as covariates: treatment groups (aQIVc, QIVc, aQIV, and QIVr), log-transformed pre-vaccination titer, age subgroup and previous vaccination history. From this model, adjusted differences in the least square means (on the log scale) will be produced with 95% confidence limits for aQIVc versus QIVc, for aQIVc versus aQIV and for aQIVc versus QIVr. The estimated difference and the confidence limits will be back-transformed to obtain an *adjusted GMT ratio* with 95% confidence limits. Each of the four strains will be analyzed separately.

The same analysis model, except excluding the factor age subgroup, will be run for each age subgroup separately and and present all adjusted GMT ratios with 95% confidence intervals for each age subgroup.

Additional exploratory analysis will be considered using age as continuous covariable including the assessment of interaction between age and treatment group.

Unadjusted GMT ratio will be based on a simple ANOVA model on the log-transformed titers and the treatment group.

Geometric Mean Fold Increase

Summary statistics (geometric mean, 95% confidence interval of GMT, minimum, median, maximum) of the relative increase in titers will be presented by assessment (Day 29), strain and vaccine group.

The analysis model for the fold increase in titers will be done using the same models as mentioned above on log-transformed (base 10) (Day 29 titers/Day 1 titers) as the outcome variable but excluding the log-transformed pre-vaccination titer.

16 MAR 2021 Final Version 2.0

Analysis of binary endpoints

The number and proportion of subjects achieving the binary endpoints (seroconversion or HI titer >=1:40) will be summarized by assessment (Day 29), strain and vaccine group.

For each of the influenza vaccine strains and for each of the vaccine groups, summaries will include the associated two-sided 95% confidence intervals according to Clopper-Pearson.

The binary endpoints (i.e. seroconversion or titer \geq 1:40) will be compared between aQIVc and each of three other vaccine group using the Miettinen and Nurminen method without adjustment for the age subgroup. The results will be presented as the difference in the percentage of subjects with 95% confidence intervals. Additional supportive analyses will be done using generalized linear models with factors for vaccine group, age subgroup as well as previous vaccination history. Adjusted differences between vaccine groups with 2-sided 95% CI will be calculated based on the model. The same analyses will be run by age group separately excluding the factor age subgroup.

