#### **Statistical Analyses:**

The primary analysis will be conducted on the immunogenicity and safety data collected up to Day 29. Exploratory comparisons of HI Geometric Mean Titer (GMTs) and MN

Print Date (Local): 30-mrt-2020 10:41:00

GMTs between treatment groups will be performed through the computation of the two-sided 95% confidence interval (CI) of the vaccine group ratio of GMTs:

*GMTs aQIVc / GMTs comparator groups*

To estimate the GMT ratio (adjusted analysis), a general linear model (GLM) will be fitted on log-transformed (base ten) post-vaccination HI titer as the outcome variable and terms for covariates: vaccine treatment, log 10 transformed pre-vaccination HI titer, age stratum, and vaccination history. Potential covariate interaction effects will also be examined in the fit of the GLM. From the model, an adjusted difference in the least square means (on the log scale) will be produced with 95% confidence limits. The estimated difference and the confidence limits will be back-transformed to obtain an *adjusted GMT ratio* with 95% confidence limits. Each of the four strains will be analyzed separately.

The difference in seroconversion rates (SCRs) or percentage of subjects with HI titer  $\geq 1:40$  will be presented with 95% CIs using the Miettinen and Nurminen method without and with adjustment for the age stratum. Each of the four strains will be analyzed separately.

Additionally, exploratory comparisons between groups will be performed through the computation of the two-sided 95% CI for the difference in the percentages between aQIVc vaccine and comparator groups.

Statistical Considerations for Sample Size Calculations:

A total of 480 subjects (including a 10% drop-out rate) will be enrolled in this study and are to be randomized in a 1:1:1:1 ratio to one of the four vaccine groups. Approximately one hundred twenty subjects will be enrolled in each vaccine group. More details on the sample size calculation are provided in [Section 8.5](#).

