### **5.1.4 Randomization**

Enrolled subjects will be randomized to one of the four treatment groups in a 1:1:1:1 ratio with stratification factors for age ( $\geq 50$  to 64 years and  $\geq 65$  years) and history of any influenza vaccination

within 3 previous influenza seasons (yes/no). Approximately 40% of subjects in each age subgroup for each treatment group should not have been vaccinated within the 3 previous influenza seasons.

The subject will be randomized in the IRT/RTSM system. The subject will receive a unique Subject ID that will be used for all eCRFs and associated study documentation for the duration of the study. After randomization, the Screening Number ceases to be used and remains in the Screening and Enrolment Log only. The list of randomization assignments is produced by the IRT service provider and approved by the Sponsor according to the applicable Sponsor's Standard Operating Procedure (SOP).

If for any reason, after signing the ICF, the subject who is eligible and enrolled fails to be randomized, this is called a randomization failure and the early termination study procedures must be applied. The reason for all randomization failures should be recorded in the Screening and Enrolment Log and in the source document. The information on subjects who are randomization failures should be kept distinct from subjects who are screen failures, as described in [Section 5.1.2](#), Screening.

If for any reason, after randomization the subject fails to undergo treatment, the subject has to be discontinued, and the reason should be recorded at the End of Study CRF. The information on discontinued subjects should be kept distinct in the source documentation from randomization failures.

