The binary endpoints (i.e. seroconversion or titer  $\geq 1:40$ ) will be compared using the Miettinen and Nurminen method without adjustment for the age stratum. The results will be presented as the difference in the percentage of subjects with 95% confidence intervals. Additional supportive analyses will be done using generalized linear models with factors for vaccine group, age subgroup, pre-vaccination titer as well as history of vaccination. Adjusted differences between vaccine groups with 2-sided 95% CI will be calculated based on the model and potential interaction effects will be examined.

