8. GENERAL ISSUES FOR STATISTICAL ANALYSES

8.1 Adjustment for Covariates

The log-transformed antibody titers at Day 29 and Day 181 will be analyzed using an Analysis of Covariance (ANCOVA) model which includes the log-transformed pre-vaccination antibody titer, age subgroup stratification (50 - 64, ≥ 65 years) and previous vaccination history stratification (no in previous 3 years, yes). Summary tables will show both adjusted and unadjusted GMTs for each vaccine group and adjusted and unadjusted GMT ratio for aQIVc versus each of the other three vaccine groups.

The main analysis of binary immunogenicity endpoints ((i.e., percentages of subjects with seroconversion and with titer \geq 1:40) will not be adjusted for any of the covariates. Binary data will be summarized for each group using unadjusted estimates and will be reported together with two-sided exact 95% CIs. Sensitivity analysis may be done to include the stratification factors age and previous vaccination history as covariates in a generalized linear model.

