16. CHANGES TO PLANNED ANALYSIS

Compared to the final protocol, one optional exploratory analysis has been added on the comparability of the cell-based and egg-based titers. Details will be described in a separate analysis plan. For the primary endpoints, the GMT and the % of subjects with HI >=1:40, Day 1 was added to assure that we include the pre-vaccination results.

The statistical analysis plan was amended before unblinding. The following changes since version 1.0 16 Jun 2020 were made:

Section	Change	Rationale
8.7	Unsolicited adverse events before	This was requested by the US
	vaccination will be mapped to medical	regulatory agency (FDA CBER).
	history	
11.2	Analysis of GMT ratio: Adjusted estimates	All subgroup analyses, including the
	of GMT ratio by age subgroup will be	age subgroup, will be conducted in a
	calculated using the same model excluding	similar way by subgroup.
	the factor age subgroup.	
11.2	Analysis of binary endpoints: Additional	Factor pre-vaccination titer was
	supportive analyses will be done using	removed from the model due
	generalized linear models without the factor	expected convergence issue leading
	for pre-vaccination titer.	to non-estimable treatment effects.
13.2	Clarification added that the temperature will	Needed for programming to apply
	be converted to °C in one decimal.	the grading for the temperature

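### The main interval for the two binary primary endpoints ignores the randomisation strata; stratifying it is a cheap and usually small gain in precision

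*SAP*

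**What the plan says.** Protocol 5.1.4 randomises "in a 1:1:1:1 ratio with stratification factors for age" and for influenza vaccination in the three previous seasons; SAP 4.1 repeats this. SAP 8.3 describes both factors as important for the immunogenicity endpoints. The GMT model in SAP 11.2 contains both, together with the pre-vaccination titre.

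For seroconversion and HI titre ≥1:40, SAP 11.2 compares aQIVc with each comparator "using the Miettinen and Nurminen method without adjustment for the age subgroup". That sentence mentions age only. The omission of vaccination history follows from SAP 8.1, where the main binary analysis "will not be adjusted for any of the covariates". Protocol 8.4.2.2.3 has the same main method: "using the Miettinen and Nurminen method without adjustment for the age stratum". SAP 11.3 carries it over to the secondary binary endpoints.

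The adjusted version is described in different ways:

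- The protocol synopsis plans the difference "using the Miettinen and Nurminen method without and with adjustment for the age stratum".
- SAP 8.1 makes the adjusted model optional: "Sensitivity analysis may be done to include the stratification factors age and previous vaccination history".
- SAP 11.2 commits to it: "Additional supportive analyses will be done using generalized linear models", with vaccine group, age subgroup and vaccination history as factors.
- SAP 16 begins "Compared to the final protocol, one optional exploratory analysis has been added" and also notes added Day 1 summaries. It does not mention the synopsis's age-adjusted Miettinen-Nurminen difference.

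**The concern.** This is an estimation study. SAP 11.2 applies no hypothesis test and Protocol 8.2 sets no success criterion, so the intervals are the result. Stratified randomisation already balances the strata between arms, which reduces the true sampling variation of the difference in percentages. An unstratified Miettinen-Nurminen interval takes no account of this. It computes the variance from the pooled rate in each arm and so counts between-stratum variation that the design has removed. If the strata are prognostic, the interval comes out too wide. What is at stake is reported precision on two of the four primary endpoint types, and on the same comparisons repeated within each age subgroup. The validity of any claim is not at stake.

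**Working it through.** **Plan's own figure.** SAP 5 gives 120 × (1 − 0.10) = 108 per arm. With SD 0.45, the detectable log10 difference is (1.96 + 0.84) × 0.45 × √(2/108) = 0.172, or a GMT ratio of 1.49. The interval multipliers are 10^(±1.97 × 0.45 × √(2/108)) = 0.76 and 1.32. Both match SAP Table 2. The documents contain no sizing figure for the binary endpoints, and Table 2 does not depend on the binary method.

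**Inputs from the documents.** 120 per arm; about half in each age group; about 40% not previously vaccinated in each age group. This gives strata of 36/24/36/24 per arm, with 10% loss.

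**Assumed.** Response rates by stratum, varied below. Order: 50–64 vaccinated / 50–64 not / ≥65 vaccinated / ≥65 not.

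**Closed form, history only, mean rate 60%.** With a the rate in vaccinated and b the rate in unvaccinated subjects:

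- Unstratified half-width: 1.96 × √(2 × 0.6 × 0.4 / 108) = 13.07 points.
- Stratified half-width: 1.96 × √(2 × [0.6·a(1−a) + 0.4·b(1−b)] / 108).
- Gap of 30 points (a = 48%, b = 78%): 12.46 points.
- Gap of 50 points (a = 40%, b = 90%): 11.32 points.

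**Simulation.** 8,000 trials per pattern with no true vaccine difference. Miettinen-Nurminen score interval with the N/(N−1) factor; the stratified version uses weights n1·n0/(n1+n0). The code returns 0.0528 to 0.3382 for the check case 56/70 vs 48/80. Half-widths are means, in points:

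| Pattern | Assumed rates (%) | Unstratified | Stratified | Loss | Coverage (%), unstratified / stratified |
|---|---|---|---|---|---|
| None | 60/60/60/60 | 12.94 | 12.95 | −0.01 | 95.3 / 95.4 |
| Mild | 55/70/50/65 | 13.02 | 12.88 | 0.14 | 95.2 / 94.9 |
| Moderate | 50/75/40/65 | 13.14 | 12.71 | 0.43 | 95.8 / 95.2 |
| High rates | 95/90/92/80 | 8.33 | 8.31 | 0.02 | 95.6 / 95.3 |
| Wide | 35/80/25/70 | 13.20 | 11.88 | 1.32 | 97.3 / 94.9 |
| Strong | 30/80/15/65 | 13.07 | 11.34 | 1.73 | 97.8 / 95.2 |

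With a true difference of +10 points (rates capped at 99%), the losses in the same order are −0.01, 0.14, 0.43, −0.05, 1.31 and 1.73.

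**Intermediate gaps.** At a mean rate of 60% and an age gap of 0 to 10 points, vaccination-history gaps of 10 / 20 / 30 / 40 / 50 points give losses of 0.05–0.11 / 0.23–0.29 / 0.53–0.58 / 0.96–1.01 / 1.50–1.55 points.

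**Where the loss sits.** The SD of the point estimate is 6.54 unstratified vs 6.53 stratified (moderate) and 5.80 vs 5.70 (strong). The loss is therefore almost entirely in the reported interval, not in the estimate.

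**Age alone.** Stratifying by age only recovers little in these patterns: 13.14 to 13.08 (moderate) and 13.07 to 12.94 (strong).

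**Within an age subgroup** (about 54 per arm, stratified by history): moderate 18.14 vs 17.67 (50–64) and 18.48 vs 17.99 (≥65); strong 18.50 vs 16.43 and 17.77 vs 15.68.

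**The case against.** The strongest reply is that an adjusted difference is already planned. SAP 11.2 commits to a generalized linear model with both factors, giving adjusted differences with 95% intervals and repeated by age group. The link and the standardisation are not stated. Assuming a logistic model with a standardised difference, 2,000 simulated trials gave mean half-widths of 12.67 points (moderate) and 11.16 (strong), against 12.71 and 11.34 for the stratified Miettinen-Nurminen interval. Coverage was about 94%. The supportive model therefore recovers nearly all of the lost width, and with no test or success criterion the label of main analysis decides nothing formally. This stands. It limits the point to which interval is presented as the main one.

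A reader might infer from the conflict between *may* in SAP 8.1 and *will* in SAP 11.2 that an adjusted result could go unreported. The documents do not support that. Protocol 8.4.2.2.3 and the change table in SAP 16 also say the model will be fitted, so SAP 8.1 is the lone outlier. The removal of pre-vaccination titre from the model is recorded and explained there, and is not a conflict.

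A reader might also infer that the SAP silently dropped a protocol analysis. The mismatch in fact begins inside the protocol: section 8.4.2.2.3 already omits the age-adjusted difference that the synopsis lists, and the SAP follows that section.

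Finally, the unstratified difference matches the crude percentages shown with Clopper-Pearson intervals. That is a fair reason to keep it in the tables, but not a reason for it to be the main comparison.

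**Conclusion.** The point holds as a modest improvement. The main binary comparison leaves out both randomisation factors, and its interval is wider than the design allows when those factors are prognostic. The excess half-width is about 0 to 0.4 points in the no-to-moderate and high-rate patterns. It reaches 1.3 to 1.7 points only with response gaps of 45 to 50 points by vaccination history. All of this rests on assumed stratum rates; nothing in the documents says which pattern applies. At rates near 100% the stratified interval can be about 0.05 points wider.

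A reader might take this to mean that the planned interval is invalid. It is not: simulated coverage is 95.2% to 97.8%, the difference is unbiased, and the method cannot create a false claim. No stated figure or decision changes.

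**What to change.** - **SAP 8.1 and 11.2:** make the main comparison the Miettinen-Nurminen difference stratified by age × vaccination history, and by history only within age subgroups. Use actual stratum values, as SAP 4.1.1 already requires, and state the stratum weights, for example n1·n0/(n1+n0).
- **Keep the unstratified difference as supportive**, with a table footnote that the two estimates can differ.
- **SAP 8.1:** change the optional wording for the generalized linear model to the commitment in SAP 11.2.
- **Synopsis:** align it with Protocol 8.4.2.2.3 and SAP 11.2, and record the outcome in SAP 16. Restoring only the synopsis's age-adjusted version would miss vaccination history, where most of the gain lies in the assumed patterns.

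The cost is SAP wording and standard programming, with no new data. The small downside is that the stratified estimate differs from the simple difference of crude percentages by 0.2 to 0.9 points on average overall, and by up to 1.2 points within an age subgroup.
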